PI/SC will serve as the visit date and time coordinator between the study pharmacist and participant. At every MTM 'visit', PI/SC will be present. The study pharmacist conducts the MTM based on the information on the case report form as well as that obtained via

participant interview. Upon completion of the interview with the participant, the study pharmacist will develop a prioritized medication problem list and create an action plan. Using sound clinical judgement and following any applicable legal and ethical practice standards, the study pharmacist will discuss/collaborate with the participant and any relevant or applicable medical provider/healthcare team member regarding the plan. Engagement (communication) with a patient's medical provider is part of the standard of care of MTM when deemed appropriate by the pharmacist performing MTM. The study pharmacist will use clinical judgement in deciding when to contact medical providers in the course of providing MTM to the participants. Included in this plan is the recommended next time point when the study pharmacist and the participant should engage for follow up. The preferred interval should not exceed 90 days (this is a data analysis plan and not a participant safety influenced interval). If at this visit (or any future visit), the study pharmacist determines additional medical records are potentially available, the study pharmacist will ensure the PI/SC seeks to attain these. Medical records will be sought for both groups by the PI/SC. If the study pharmacist feels compelled to obtain complete medical records for those randomized to the control group, this is allowed. The study pharmacist would be acting outside of the role of the study pharmacist in this regard and would have to obtain a separate release of medical records using Walgreen's standards to obtain this. Costs associated with this would fall to the study pharmacist or participant. The study pharmacist would be required to communicate this information to the participant. This would impact how that participant's data is managed thereafter but does not require discontinuation from the study. This is detailed later in the protocol, section F.1. This is also provided in the consent in Alternative Treatment section.

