2) **Data Analysis and Data Monitoring** – Describe plans for statistical analysis of data when appropriate. If a data safety monitoring committee is appropriate to protect the safety and/or welfare of subjects, describe its operation (e.g., membership, stopping rules and frequency of review).

The diseases being used to validate HIV-CMTM effectiveness are HIV, DM and HTN. For HIV, disease control is defined as plasma HIV-RNA of < 20 copies/mL. Standard of care recommends follow-up based on viral load. (19) For DM, self-monitoring of blood glucose is less reliable than quarterly A1c levels (goal of \leq 7%) which is monitored every 3 months. In HTN, goals vary based on comorbid conditions as follow-up varies with medications. As AA have 2-3 higher incidental rates of stroke compared to whites. (Howard). As a 10 mmHg difference in systolic blood pressure is shown to reduce stroke rate by 24% in AA, a decrease in systolic blood pressure reductions of 10 mmHG [or attainment of blood pressure goal] was selected as the primary measure for effectiveness on HTN. Medical record blood pressure will be the primary source for analyses as ultimately, it is the information collected by the diagnostician that is used for decisions.

Two sample t-test for continuous outcomes (viral loads) and chi-square for categorical outcomes (blood pressure under control or not) would be used to assess significance at the 0.05 level.

DATA AND SAFETY MONITORING PLAN

There are no medical procedures or prescription changes that can occur as part of this study that are not first authorized by the patient's medical provider. A data safety monitoring plan has been presented and approved by the NIMHD Program and Science Officer that reflects the low safety risk to participants, from a medical perspective. The **DATA SAFETY PLAN** is attached. The risks to participants due to protection of information and how information is safely maintained is addressed elsewhere in the protocol.

3) **Data Storage and Confidentiality**

Data Security, Collection, Entry, Management, and Quality Control: Only authorized study personnel will have access to the data. All HIPAA research safeguards and protocols for protected health information will be observed. All randomized participants will be assigned a unique identification (UID) number for use throughout the project. This number will be

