Two hundred adult AA with HIV and either/both DM or HTN will be recruited using NTRIRB approved recruitment materials. Once consented, patient gender and comorbidity stratified randomization (i.e., separate randomization by men/women and by DM/HTN) will be used to randomize them into the intervention group or control. Randomization assignment will be controlled by the biostatistician. This will create eight groups: men with DM receiving intervention (1.a.), men with DM receiving control (2.a.), women with DM receiving intervention (1.b.), etc. (Figure 4). Patients with dual diagnosis of DM and HTN will be randomized into either the intervention or control group. Their data will be used in both DM and HTN analyses (after conducting a sensitivity analysis to determine that the dual diagnosis does not confound or bias the results). A random number generator (range 1 to 10,000) will be used for group assignment. UNTHSC biostatistician will be the only unblinded member of the research team to which number corresponds to the intervention or control groups when presenting data during investigator team safety reviews and data safety monitoring plan described.

The primary endpoint for this study will be the health indicators collected at the final follow-up visit comparing the corresponding intervention and control groups (e.g., intervention vs. control for men with diabetes). We computed the power and sample size based on the effect sizes estimated from our previous CDC-funded demonstration project where observations from 201 African American HIV patients at baseline whose viral loads were either detectable (>20 copies/mL) or their CD4 counts were <200 cells/mcL at baseline. Of these, 171 (85%) showed improvement (viral loads became undetectable or CD4 counts became >200 cell/mcL) at follow-up after receiving quarterly HIV-CMTM. Based on these results and even assuming a very conservative effect of 45% improvement for the control group receiving standard of care projects that a comparison between intervention and control will require 22 subjects per group. This enrollment volume enables attaining a power of at least 80% at the 0.05 level of significance for each of the comparisons. As some attrition is expected, we will recruit 25 patients per group for a total of 200 patients. We also note that the sample sizes are very likely larger as the subjects with a dual diagnosis of diabetes and hypertension will be included in the analyses, but are not included in the

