sample size computations shown above. We also conducted additional power analyses based on this sample size to verify that the analyses will be sufficiently powered when the outcome measures are treated as continuous (testing means) rather than dichotomous.

Control Group Medical Record Viewing by Study Pharmacist

Pharmacists are not prohibited from requesting the complete medical record from a medical provider pursuant to normal counseling and care provided, this is just rarely (if ever) done. Pharmacists routinely contact medical providers to recommend changes to medications. If the study pharmacist, in the course of providing MTM to participants in the control group, contacts a medical provider, this will not change the status of the control group participants. If, however, the study pharmacist feels compelled to obtain the entire medical record for a participant in the control group, s/he will notify the participant and PI/SC. Should the study pharmacist inadvertently gain access to a control participant's medical records (participant brings medical records themselves to the MTM session and the study pharmacist uses the complete medical record for the purposes of MTM), the participant will not be discontinued. In either case, the participant will not be discontinued. The time point at which the study pharmacist gained access to the medical record for participants in the control group will be noted and this will become a controlled variable in the analyses.

2) Describe both *Inclusion AND Exclusion Criteria*.

Inclusion criteria:

- >/= 18 years old or older at time of screening
- Male or female
- Self identifies as African-American or black
- Able to read and speak English sufficiently well enough to be interviewed by study pharmacist (as determined at screening visit by PI/SC)
- Confirmed diagnosis of HIV (medical record)
- Confirmed diagnosis of diabetes, hypertension, or both (medical record)
- Stated agreement to comply with study requirements during screening visit
- Able and willing to provide written informed consent
- Willing to notify study pharmacist if becomes pregnant during study
- Expresses a willingness to participate in all study-related assessments and adhere to study requirements
- Willing to notify research team if planning to relocate
- Willing to notify research team if incarcerated at any point during study

Exclusion criteria: (whether discovered at time of consent or after review of medical records)

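### Record access, a post-randomisation event noted only for controls, is to be adjusted for in the analyses, and the primary comparison is not exempted

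*Combined protocol and SAP*

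**What the plan says.** All references are to the combined protocol and SAP.

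- **E.1, Visit 2.** "If the study pharmacist feels compelled to obtain complete medical records for those randomized to the control group, this is allowed". Such access affects how the participant's "data is managed thereafter but does not require discontinuation from the study. This is detailed later in the protocol, section F.1".
- **F.1, Control Group Medical Record Viewing by Study Pharmacist.** A second route is that the "participant brings medical records themselves to the MTM session and the study pharmacist uses the complete medical record". For both routes: "In either case, the participant will not be discontinued". The only analysis rule is that the time of access "for participants in the control group will be noted and this will become a controlled variable in the analyses". The section expects that a pharmacist's request for the full record will be uncommon: "this is just rarely (if ever) done".
- **F.1, Sample Size.** "The primary endpoint for this study will be the health indicators collected at the final follow-up visit", comparing intervention with control within groups such as men with diabetes.
- **E.2, Data Analysis and Data Monitoring.** "Two sample t-test for continuous outcomes (viral loads) and chi-square for categorical outcomes (blood pressure under control or not) would be used", at the 0.05 level.

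The available text does not mention intention-to-treat, analysis as randomised, an analysis population, or a sensitivity analysis for record access.

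**The concern.** Randomisation makes the arms comparable at entry. Record access comes later. It depends either on a pharmacist's judgement that the record is needed or on a participant's initiative in bringing it, and both may be related to prognosis or engagement. No intervention participant can carry a variable that is noted only for controls. Adjusting for it therefore cannot balance the arms; it changes which controls the intervention arm is compared with. The adjusted effect equals an uncontaminated treatment effect only if controls with access resemble the other controls, and nothing in the documents supports that.

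The text also conflicts with itself. The tests named in E.2 cannot hold a covariate, while F.1 requires one in the analyses without saying which analyses or in what form. Unless this is settled in writing, whether and how to adjust is still open when outcomes are compared by arm.

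**Working it through.** **1. The plan's own figure.** F.1 gives 22 per group for 85% vs 45%, 80% power, 0.05. With a pooled variance, two-sided (assumed) and no continuity correction:

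n = [1.960·√(2·0.65·0.35) + 0.842·√(0.85·0.15 + 0.45·0.55)]² / 0.40² = (1.322 + 0.515)² / 0.16 ≈ 21.1, so 22.

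The figure reproduces, and this point does not change it. F.1 recruits 25 per group.

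**2. What the adjustment does.** Take a linear model with arm T and access variable A.

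- *A is zero for everyone without access, one accessed control.* The coefficient of A fits that person exactly, so the remaining participants alone determine the arm effect. In one simulated cell of 25 per arm, coding A as 1, 3, 5 or 8 gave −9.958 each time. Deleting that control gave −9.958; the as-randomised difference was −8.598.
- *Several accessed controls, ever/never coding.* The same holds. With 15 of 100 controls accessed, the adjusted estimate was 0.0338, the estimate after deletion 0.0338, and the as-randomised estimate −0.1499. Because the endpoint is taken at the final visit, an on/off variable switching at access equals ever/never there.
- *Several accesses, coded by time since access.* Removal is partial: about 79% of the ever/never shift at 1–4% access, with access times assumed uniform over 1–8 quarters.
- *Other codings.* Suppose A is a visit number: 2 for intervention participants, 9 for never-accessed controls, 5 for one accessed control. Three distinct (T, A) pairs and three coefficients give: arm effect = (intervention mean − never-accessed mean) + 7 × gap / (5 − 9), where gap = accessed outcome − never-accessed mean. An assumed gap of 10 mmHg moves the estimate by 7 × 10 / (−4) = −17.5 mmHg, which has no useful interpretation.

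**3. Size under zero coding.** The documents give no access rate and no outcomes for accessed controls, so these inputs are assumptions.

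*Continuous outcome.* With ever/never coding the shift is f × gap, f being the fraction of controls with access. For a gap of 10–15 mmHg of either sign, it is 0.10–0.15 mmHg at 1% and 0.40–0.60 mmHg at 4%. With SD 18 and 25 per arm, SE = 18·√(2/25) = 5.09 mmHg, so the 4% shift is 8–12% of the SE.

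*Binary outcome, one access among 22 controls.* If 10/22 are at goal (near the planned 45%), the control rate becomes 9/21 (−2.6 points) or 10/21 (+2.2 points). The SE is √(0.45·0.55/22 + 0.85·0.15/22) = 13.1 points, so the shift is 17–20% of it.

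*How often the 0.05 verdict changes.* I enumerated every outcome with 22 per group and control rate 45%, comparing the uncorrected chi-square with and without the accessed control. The results were averaged over goal status (45% at goal, 55% not) and multiplied by the probability of exactly one access among the 25 recruited controls: 25·0.01·0.99²⁴ = 0.196 and 25·0.04·0.96²⁴ = 0.375.

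| Intervention rate | Input: at goal | Input: not at goal | Average | 1% access | 4% access |
|---|---|---|---|---|---|
| 85% | 6.37% | 1.78% | 3.85% | 0.8% | 1.4% |
| 75% | 11.75% | 0.66% | 5.65% | 1.1% | 2.1% |
| 70% | 11.59% | 0.31% | 5.39% | 1.1% | 2.0% |
| 65% | 9.93% | 0.16% | 4.56% | 0.9% | 1.7% |

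First row: 0.45 × 6.37% + 0.55 × 1.78% = 3.85%; × 0.196 = 0.8%; × 0.375 = 1.4%. Only the last two columns are results. The input columns are conditional and depend on cell size: with 25 per group their order reverses, while the results stay similar (0.6–1.3% and 1.2–2.4%).

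Cells with two or more accesses are left out. At least one access has probability 1 − 0.99²⁵ = 0.222 or 1 − 0.96²⁵ = 0.640, so the omitted cells are about 3% of all cells at 1% access and 26% at 4%.

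**The case against.** The strongest reply is that the plan already points to an unadjusted comparison. F.1 compares the randomised groups, E.2 names only tests without covariates, and accessed controls are retained and still called control participants. On that reading, access belongs to some further analysis. The reply stands in part: a reader might infer that the plan orders a non-randomised primary analysis, and the documents do not go that far. But the sentence in F.1 is a commitment covering the analyses without exception, and E.2 and the sample-size text conflict with it rather than override it.

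The data safety plan, to which the protocol refers for more detail, is not in the available text. Absence can therefore be asserted only for what is available. An unseen attachment does not alter the rule stated in F.1.

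Three stronger readings are tempting and are not supported:

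- *That any form of the variable amounts to deleting the accessed control.* This holds only for codings that are zero for everyone else, and the plan gives no coding.
- *That one access is likely to overturn a result.* A cell close to 0.05 can be made to cross it, but whether it crosses depends on the test chosen, and such a case says nothing about frequency.
- *That type I error is badly inflated.* Simulation at 100 per arm gives 17.1% adjusted against 5.4% unadjusted only with 20% access and a 15% success rate among accessed controls. At 5% access with the same success rate it is 5.7% against 5.4%. The plan expects access to be rare.

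**Conclusion.** The concern holds as a conflict in the stated analysis rules, with a probably small numerical effect. Applied as written with zero coding, the F.1 rule takes accessed controls wholly or largely out of the arm contrast, although the same section keeps them in the study. Other codings can give estimates with no clear meaning.

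The direction cannot be derived from the documents. About 1–2% of cells would change verdict, given assumed access of 1–4%, exactly one access in the cell, a control rate of 45% (which the plan sets for a viral load/CD4 outcome), accessed controls at goal as often as other controls, and an uncorrected chi-square. If no access occurred, the point is moot. The sponsor should still correct it, because the remedy is cheap and closes an analysis choice that could otherwise be made with outcomes in view.

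**What to change.** In F.1, replace the sentence that makes access a controlled variable with:

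> The primary analysis compares all participants in the arm to which they were randomised, without adjustment for record access. The number, timing and route (pharmacist request or participant-supplied) of control-group accesses will be reported. Any access-adjusted analysis is a sensitivity analysis, with the form of the variable defined before outcomes are compared by arm.

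Make the Visit 2 text in E.1 agree with this, and state that the as-randomised estimate includes any dilution from control access. If no access occurred, report that; no adjusted analysis is then needed.

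The cost is a few sentences. No new data, visits or consent are needed: the time of access is already noted, and the route can be taken from the pharmacist's notice to the study team or from the team's presence at visits.

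The statistical cost is the dilution. If access gave full benefit, 4% access would remove 0.04 × 10 = 0.4 mmHg from an assumed 10 mmHg effect. For the binary outcome, 5% access with accessed controls reaching 85% raises the control rate to 0.45 + 0.05 × 0.40 = 47%. Power then falls from 81.7% to 77.8% at 22 per group, or from 86.6% to 83.1% at 25.
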